With increasing volume and complexity of cardiac interventional procedures requiring venous access, venous hemostasis and subsequent groin complications are a significant concern. The MynxGrip VCD appears to be an excellent choice for venous closure due to its extravascular use of a water-soluble, polyethyleneglycol matrix. In a recent large, single center study, propensity score-matched analysis, the MynxGrip device was successfully deployed in the femoral vein for immediate hemostasis. Results showed consistent safety and efficacy, similar to arterial device deployment, with low complication rates (<1%) and no major bleeding events. Importantly, no vessel injury or deep vein thrombosis were noted⁵. The ability to achieve rapid and reliable venous hemostasis following either a diagnostic or interventional procedure appears feasible, although no device has FDA approval for such an indication.

STUDY AIM

This study is aimed to assess safety of the MynxGrip™ Vascular Closure Device (VCD) [AccessClosure, Mountain View, CA] system for venous access site hemostasis following diagnostic and interventional procedures.

HYPOTHESIS

1. The MynxGrip™ Vascular Closure Device is as safe as manual compression for venous hemostasis following diagnostic or interventional procedures.

OBJECTIVES

PRIMARY

1. Evaluate the safety of the MynxGrip extravascular sealant for common femoral vein closure following both diagnostic and interventional procedures as assessed by clinical and imaging criteria.

ENDPOINTS

**The Safety and Efficacy of an Extravascular,
Water-Soluble Sealant for Venous Access-site Closure**

PRIMARY

The primary safety endpoint will include both deep venous thrombotic and bleeding/vascular injury related complications prior to discharge and at 1 week follow-up. Outcomes will be assessed via clinical evaluation and imaging with clinically indicated as follow:

- Assessment of venous thrombosis
 - i. Clinical: Physical exam findings consistent with venous thrombotic/thromboembolic related complication:
 - Redness or swelling at the venous puncture site
 - Increased lower extremity edema
 - Calf pain
 - New onset or worsening shortness of breath
 - New onset of pleuritic chest pain
 - ii. and if clinically indicated, imaging: venous Doppler ultrasound assessment of obstructive or non-obstructive deep vein thrombosis (DVT)
- Bleeding or vascular related complications
 - i. Damage to the vessel requiring surgical repair
 - ii. Access site bleeding requiring the need for transfusion
 - iii. Nerve injury at access site
 - iv. Generalized infection (septicemia with typical signs, symptoms and positive blood cultures shortly after the index procedure, and requiring treatment with intravenous (IV) antibiotics)Pseudo-aneurysms requiring invasive treatment
- Device/procedure failure
 - Device failure is defined as either the inability to deploy the device or device deployment with inadequate hemostasis requiring conversion to immediate manual pressure, or the eventual need for alternative methods to obtain hemostasis.

.Efficacy will be assessed by time to hemostasis:

Time to hemostasis is defined as the time from advance tube removal (i.e., device removal) to the time when hemostasis was first observed.

STUDY POPULATION

NUMBER OF SUBJECTS

A total of 208 patients undergoing either diagnostic or interventional procedures will be enrolled into this trial.

ELIGIBILITY OF SUBJECTS

GENERAL INCLUSION CRITERIA

**The Safety and Efficacy of an Extravascular,
Water-Soluble Sealant for Venous Access-site Closure**

Patients > 18 years of age scheduled for a percutaneous diagnostic or interventional procedure that have either a 5, 6, or 7F sheath placed in the common femoral vein.

EXCLUSION CRITERIA

1. Patient has a history of a bleeding disorder
2. Previous history of venous thrombosis or thromboembolism
3. Patient is pregnant or lactating
4. Patient has a known severe allergy to contrast medium
5. Patient has a known allergy to PEG
7. Patient is known to require an extended hospitalization or re-hospitalization (e.g. patient is undergoing coronary artery bypass graft (CABG) surgery) or patient is scheduled to have a CABG surgery <30 days following the procedure)
9. Multiple (>1) attempts at venous access were attempted
10. Patient has intra-procedural bleeding around the access site prior to sheath removal
11. Critically ill patients requiring intravenous vasopressors for blood pressure stabilization
12. Ipsilateral femoral artery puncture or sheath insertion
13. Glycoprotein IIb/IIIa use
14. Any bleeding or vascular access-site complication evident pre-venous closure

STUDY DESIGN

OVERVIEW

The polyethylene glycol (PEG) sealant utilized for arteriotomy site closure in the MynxGrip system was previously demonstrated to be safe and effective in the Matrix VSG study, a prospective, randomized, 500-patient proof of concept trial at 13 US centers. Furthermore, the pivotal trial demonstrated absence of major complications requiring surgical repair, low minor complication rates without need for additional intervention or hospitalization, rapid time to hemostasis regardless of ACT levels or anti-coagulant use, and high device success rates (4).

MynxGrip is currently an FDA approved VCD for arterial use, with a venous indication currently in review by the FDA. No technique change is proposed for the venous study. Hence, this is primarily a safety study for the MynxGrip extravascular, water-soluble sealant vascular closure device for use in venous hemostasis.

The study will be conducted entirely at the MedStar Washington Hospital Center. Following either diagnostic or interventional procedures where venous access was required (via the common femoral vein with insertion of either 5, 6, or 7F sheath), femoral vein hemostasis will be achieved with either manual compression or the MynxGrip VCD system. A total of 208 patients will be prospectively enrolled in this study and will be followed for 7 days post procedure for safety purposes. To assess the primary safety outcome of venous patency and lack of occurrence of DVT, clinical assessment will be performed by the study team vascular access assessment group

The Safety and Efficacy of an Extravascular, Water-Soluble Sealant for Venous Access-site Closure

and when clinically indicated a duplex ultrasound will be performed on patients prior to discharge to evaluation the presence of venous thrombosis. Patients will have final post-procedure telephone follow-up at 7 days to assess clinical findings consistent with any vascular or bleeding complications.

After enrollment, subjects will be randomized 1:1 to:

- Treatment Group A: Subjects will have venous hemostasis achieved using the MynxGrip vascular closure system in the common femoral vein.
- Treatment Group B: Subjects will have venous hemostasis achieved using manual compression over the common femoral vein.

Subjects who meet all inclusion criteria and none of the exclusion criteria, who agree to participate in this clinical study, and who sign an informed consent will be enrolled.

Statistial Analysis

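### The Overview names venous patency and absence of DVT as the primary safety outcome, but ultrasound only when clinically indicated supports non-inferiority for clinically evident thrombosis, not for patency or any DVT

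*Combined protocol and SAP*

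**What the plan says.** The combined protocol and SAP describes the thrombotic part of the primary outcome in several places.

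- **Study Design, Overview.** The outcome and its measurement are given together: "To assess the primary safety outcome of venous patency and lack of occurrence of DVT, clinical assessment will be performed". Imaging is conditional: "when clinically indicated a duplex ultrasound will be performed on patients prior to discharge". The last contact is remote: "Patients will have final post-procedure telephone follow-up at 7 days to assess clinical findings consistent with any vascular or bleeding complications".
- **Endpoints, Primary.** The general rule is "Outcomes will be assessed via clinical evaluation and imaging with clinically indicated as follow". A list of signs and symptoms follows, and then, where clinically indicated, "venous Doppler ultrasound assessment of obstructive or non-obstructive deep vein thrombosis (DVT". The window runs to the 1-week follow-up.
- **Objectives, Primary.** Safety is to be evaluated "as assessed by clinical and imaging criteria".
- **Sample Size Calculation.** The non-inferiority comparison is sized on venous thrombosis, not restricted to symptomatic events. It assumes 2.4% in both arms, a margin of 5%, α of 0.05 and 104 patients per arm.

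No section plans a routine scan, says what makes a scan clinically indicated, or limits the conclusion to clinically evident thrombosis.

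**The concern.** Patency is an imaging finding, and a thrombus that does not obstruct flow may give no sign on examination. The plan names both but obtains an image only in patients whose condition prompts one. In the rest, the outcome as worded is not observed.

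In a superiority trial, missing the same share of events in both arms usually works against the new treatment. In a non-inferiority trial with an absolute margin it works the other way: the observed difference shrinks and the margin does not. A finding that the device is non-inferior for DVT or patency could then be reached although the true excess of any DVT is as large as the margin. The Overview calls this primarily a safety study, so the scope of that sentence is the main thing the trial delivers.

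**Working it through.** **1. The plan's own figure.** The unpooled-variance formula is n per arm = 2p(1−p)(z₁₋α + z_power)²/δ², with p = 0.024 and δ = 0.05. At one-sided 0.05 it gives 101 at 75% power, 116 at 80% and 161 at 90%. Power and sidedness are not stated, so 104 cannot be reproduced from the document alone. It corresponds to 76.1% power at one-sided 0.05 or 65.4% at one-sided 0.025. That is a separate matter; here 104 per arm is simply taken as planned.

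**2. Expected events.** 104 × 0.024 = 2.5 per arm if every thrombus is found.

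**3. Effect of incomplete detection.** Let s be the share of thrombi detected, equal in both arms, with no false positives. The documents do not give s. True rates π_D (device) and π_C (control) are observed as sπ_D and sπ_C, so a true 5-point excess appears as 5s points. At s = 0.5 it appears as 2.5 points, still judged against 5.

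**4. Chance of declaring non-inferiority when the true excess equals the margin.** The plan names no test. I assumed non-inferiority is declared if

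p̂_D − p̂_C + z·√{[p̂_D(1−p̂_D) + p̂_C(1−p̂_C)]/104} < 0.05,

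and summed the two binomial distributions exactly over all outcomes meeting that rule. Two readings of the 2.4% are possible:

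- **Reading A:** 2.4% is the fully detected any-DVT rate. True rates are 7.4% v 2.4%, observed as 7.4s v 2.4s.
- **Reading B:** 2.4% is the clinically detected rate. The control arm is observed at 2.4% and the device arm at 2.4 + 5s. At s = 0.5 the true rates are 9.8% v 4.8%, observed as 4.9% v 2.4%.

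| s | A, z = 1.645 | A, z = 1.96 | B, z = 1.645 | B, z = 1.96 |
|---|---|---|---|---|
| 1.00 | 6.5% | 3.7% | 6.5% | 3.7% |
| 0.75 | 15% | 10% | 14% | 9% |
| 0.50 | 34% | 28% | 27% | 19% |
| 0.25 | 72% | 70% | 48% | 38% |

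At s = 1 the result is above the nominal 5% (or 2.5%) because of the Wald limit at low rates, so the detection effect is the rise from that first row.

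**5. What a result with no events would mean.** If both arms truly have 2.4%, the chance of no detected DVT among 208 patients is (1 − 0.024s)^208: 0.6% at s = 1, 8% at s = 0.5 and 29% at s = 0.25. Without knowing how many patients were scanned, a report of no DVT is hard to interpret.

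**The case against.** Symptom-driven ascertainment of DVT is a legitimate design choice, and the plan states it openly in both places where it describes assessment. Patency appears once, in the Overview; the Endpoints section speaks of complications and does not mention it. The reference to non-obstructive DVT sits inside the conditional imaging clause, so it can be read as saying what counts when a scan is done. The stated hypothesis is that the device is as safe as manual compression, and no section announces a separate patency claim. The numbers depend on an assumed s, a test the plan does not name, an uncertain meaning of 2.4%, and a model of DVT alone although the endpoint has other components.

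Much of this stands. A reader might infer that silent thrombus is never measured, or that every unscanned patient is counted as having a patent vein. The documents do not support either. What triggers a scan is undefined, and the listed signs include local redness or swelling, which could prompt a scan that shows non-obstructive thrombus. No counting rule for unscanned patients is given.

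It is also true that rewording alone leaves the same data, rate and margin in place. And if imaging confirmation were required, symptoms first reported at the day-7 call could drop out, because no imaging pathway after that call is stated.

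What remains is that the Overview names an outcome the planned measurements do not systematically capture, and nothing else in the document narrows the claim.

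**Conclusion.** The mismatch is real and should be fixed before analysis, but it is a matter of scope and does not invalidate the design. As planned, the trial can address clinically evident venous thrombosis and the bleeding and vascular components. It cannot support non-inferiority for patency or for any DVT.

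The direction is firm: for any s below 1, equal in both arms, under-detection moves the comparison towards non-inferiority. The size is not. At half detection and one-sided 0.05 the illustrative chance is 34% or 27%, against 6.5% at full detection, depending on how the 2.4% was ascertained. It would be tempting to quote these, or the 72% at s = 0.25, as the trial's actual error rate. The documents do not support that, because they give neither the sensitivity nor the test. The calculation also assumes equal detection in the two arms, and no masking of the assessment is described.

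**What to change.** 1. In the Overview, delete the reference to patency. There and in Endpoints, Primary, define the thrombotic component as clinically evident venous thrombosis.
2. Report suspected events both with and without imaging confirmation, so that unconfirmed symptoms from the day-7 call are not silently treated as non-events.
3. State that asymptomatic thrombus is not assessed and that the non-inferiority claim does not extend to patency or to any DVT.
4. In the Sample Size Calculation, confirm that the 2.4% rate and the 5-point margin apply to clinically evident thrombosis, or restate and justify them. Without this step the rewording corrects the claim but leaves the margin unexamined.
5. Report the number and proportion of patients imaged in each arm beside the primary result.

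The cost is protocol wording, a short justification of the rate and margin, and one extra table. The downside is a narrower claim. If the rate or margin has to be restated, the sample size will need to be recalculated.
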